3.7 Procedures related to neutropenia

During the two phase 1 trials with 1790GAHB, two subjects of African descent experienced a transient and clinically asymptomatic decrease of circulating neutrophils of

grade 3 (severe) that was finally classified as "benign ethnic neutropenia". In addition, six more subjects experienced transient and clinically asymptomatic grade 2 (moderate) neutropenia. Although this finding was not associated with any clinical illness, some precautionary procedures for enrollment and monitoring of trial subjects were introduced to protect the safety of study subjects, including selection of subjects with baseline ANC above $1.8 \times 10^9/L$.

In order to maintain a prudent approach, but, at the same time, to not compromise the scientific validity of the clinical trial by selecting participants that are not entirely representative of the local healthy population (if non-local laboratory reference intervals are used) a step-wise approach will be adopted for the present trial H03_04TP. More specifically, same as in Phase 1 trials, the more conservative western normal ranges will be adopted for ANC collected up to 7 days after 1st vaccination of the initial 18 subjects.

Subsequently, all safety data from these 18 subjects will be evaluated by the DSMB which will make a recommendation as to whether the enrollment and assessment of neutropenia during the study of further subjects could be done using the local normal ranges published for neutrophils (Karita et al., 2009) and for which a consensus interval of 1.0 to $5.3 \times 10^9/L$ has been reached, or should be continued using the western normal ranges adopted for the first 18 subjects. This is also in consideration of the clinically benign nature of the events reported in the phase 1 studies and of the documented lower absolute neutrophils counts in healthy African populations (one of the key targets for this vaccine) compared to western populations (Badenhorst et al., 1995, Ezeilo, 1972, Lugada et al., 2004),

Therefore, study procedures will be as follows:

- First subset of 18 subjects (prior to DSMB evaluation of data):

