Subjects with ANC less than $1.8 \times 10^9/L$ at screening will not be enrolled in the study. All individuals with ANC $< 1.8 \times 10^9/L$, occurring at 7 days after the first dose, will have additional blood draws for complete blood count to be repeated on a weekly basis until the neutropenia resolves ($ANC \geq 1.8 \times 10^9/L$). In case the ANC is less than $0.5 \times 10^9/L$ after 1st vaccination, the subject will be immediately discontinued from 2nd vaccination and will have the test repeated on a weekly basis until the neutropenia resolves.

- All subjects (after DSMB evaluation of safety data from the initial 18 subjects with recommendation to switch to local normal ranges published for neutrophils):

Subjects with neutropenia defined as ANC less than $1.0 \times 10^9/L$ at screening will not be enrolled in the study. All individuals with a neutropenia ($ANC < 1.0 \times 10^9/L$), occurring

at any time during the study 7 days after the first dose, will have additional blood draws for complete blood count to be repeated on a weekly basis until the neutropenia resolves ($ANC \geq 1.0 \times 10^9/L$). In case the ANC is less than $0.5 \times 10^9/L$ after 1st vaccination, the subject will be immediately discontinued from 2nd vaccination and will have the test repeated on a weekly basis until the neutropenia resolves.

For classification and grading of severity of neutropenia for the first subset of 18 subjects, the criteria of Common Terminology Criteria for Adverse Events (CTCAE) issued by US Department of Health and Human Services (version 4.3; 2010) will be adopted. In case DSMB endorses the use of local ranges of normality for the second subset of 54 subjects, the grading will be modified based on input from DSMB. All individuals with neutropenia either ongoing or with onset at visit 5 (or last study visit) will have additional blood draws for complete blood count to be repeated on a regular basis until the neutropenia resolves ($ANC \geq 1.0 \times 10^9/L$ or $ANC \geq 1.8 \times 10^9/L$, depending on recommendations given by DSMB after evaluation of safety data from the initial 18 subjects).

Finally, all cases of neutropenia, regardless of intensity, will be considered as Adverse Events of Special Interest (AESI) from a reporting perspective.

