7.1.4 Serious Adverse Events

A serious adverse event (SAE) is defined as any untoward medical occurrence that at any dose results in one or more of the following:

- Death.
- Is life-threatening (i.e., the subject was, in the opinion of the investigator, at immediate risk of death from the event as it occurred); it does not refer to an event which hypothetically might have caused death if it were more severe.
- Required or prolonged hospitalization.
- Persistent or significant disability/incapacity (i.e., the event causes a substantial disruption of a person's ability to conduct normal life functions).
- Congenital anomaly/or birth defect.
- An important and significant medical event that may not be immediately life threatening or resulting in death or hospitalization but, based upon appropriate medical judgment, may jeopardize the subject or may require intervention to prevent one of the other outcomes listed above.

Adverse events which do not fall into these categories are defined as non-serious.

It should be noted that a severe adverse event need not be serious in nature and that a serious adverse event need not, by definition, be severe.

Serious adverse events will be captured both on the Vaccines Serious Adverse Event (VSAE) form as well as on the AE CRF. All SAEs will be evaluated by the investigator for relationship of the event to study vaccine. SAEs that are judged to be possibly or probably related to the study vaccine should be reported to the Sponsor as related/suspected events.

The relationship of the study treatment to an SAE will be determined by the investigator based on the following definitions:

1. Related/suspected

The SAE is judged by the investigator to be possibly or probably related to the study vaccine on the AE CRF page (see [section 7.1.3, Evaluation of Adverse Events](#)).

2. Not Related

The SAE is not related if exposure to the study vaccine has not occurred, **or** the occurrence of the SAE is not reasonably related in time, **or** the SAE is considered unlikely to be related to use of the study vaccine, i.e., there are no facts (evidence) or arguments to suggest a causal relationship.

The relationship of the study vaccine to an SAE will be determined by the investigator.

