7.1.4.1 Adverse Events of Special Interest

Adverse events of special interest (AESIs) are predefined adverse events that will be specifically highlighted to the investigator and will be summarized separately at the end of the study. All AESIs occurring during the study will be categorized and reported as a SAE.

Reactive arthritis (ReA) will be collected and analyzed as an AESI for this study.

Reactive arthritis is defined as non-purulent joint inflammation that develops in response to an infection in another part of the body. Since the inflammation is triggered by a previous condition, it is termed “reactive”. Intestinal pathogens that have been associated with reactive arthritis include *Campylobacter*, *Salmonella*, *Yersinia*, *Clostridium difficile*, and *Shigella*. If reactive arthritis is caused by an auto immune response, there is at least a possibility that it could be initiated by vaccination of susceptible people with the 1790GAHB vaccine.

For diagnosis of ReA, imaging and aspiration are not required (unless clinically indicated).

Neutropenia, a decrease of circulating neutrophils below the lower limit of the range of normality, will be collected and analyzed as an AESI for this study. To this purpose, as specified in the study procedures, subjects in this trial will have multiple blood draws for monitoring potential episodes of post vaccination neutropenia. For additional information on neutropenia, please refer to Section 3.7, Procedures Related To Neutropenia

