8. STATISTICAL CONSIDERATIONS

8.1 Endpoints

8.1.1 Primary Endpoint(s)

8.1.1.1 Primary Safety Endpoint(s)

The safety profile of the two vaccine doses and control(s) will be assessed through measurement of the following:

- a. Number and percentage of subjects with solicited local and systemic adverse reactions during 7 days following each vaccination.
- b. Numbers and percentage of subjects with deviations from normal ranges of safety laboratory data after each vaccination.
- c. Number and percentage of subjects with reported unsolicited adverse events during 28 days following each vaccination.
- d. Number and percentage of subjects with reported SAEs throughout the study duration.
- e. Number and percentage of subjects with reported reactive arthritis or neutropenia (AESIs).

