8.4.2.1.3 Analysis of Unsolicited Adverse Events

This analysis applies to all adverse events occurring during the study, judged either as probably related, possibly related, or not related to vaccination by the investigator, recorded in AE CRF, with a start date on or after the date of first vaccination. AE starting prior to the first vaccination will only be listed. The original verbatim terms used by

investigators to identify adverse events in the CRFs will be mapped to preferred terms using the MedDRA dictionary. The adverse events will then be grouped by MedDRA preferred terms into frequency tables according to system organ class (SOC).

All reported adverse events, as well as adverse events judged by the investigator as at least possibly related to study vaccine, will be summarized according to SOC and preferred term within SOC. These summaries will be presented by vaccination group. When an adverse event occurs more than once for a subject, the maximal severity and strongest relationship to the vaccine group will be counted.

Separate summaries will be produced for the following categories:

- Serious adverse events and adverse events of special interest.
- Adverse events that are possibly or probably related to vaccine.
- Adverse event leading to withdrawal.

Data listings of all adverse events will be provided by subject. In addition, adverse events in the categories above will be provided as listed data.

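### The top-line SAE counts for primary endpoint (d) would mix laboratory neutropenia with events that meet the protocol's own seriousness criteria

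*Protocol*

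**What the plan says.** **Protocol 7.1.4** lists six seriousness criteria and then says: "Adverse events which do not fall into these categories are defined as non-serious".

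**Protocol 7.1.4.1** overrides this for AESIs: "All AESIs occurring during the study will be categorized and reported as a SAE". It defines neutropenia as an AESI by the laboratory value alone, a count below the lower limit of normality, with no requirement for symptoms. It also commits to summarizing AESIs separately at the end of the study.

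**Protocol 3.7** adds that "all cases of neutropenia, regardless of intensity, will be considered as Adverse Events of Special Interest (AESI) from a reporting perspective". The lower limit is 1.8 × 10⁹/L for the first 18 subjects. The DSMB then makes a "recommendation as to whether the enrollment and assessment of neutropenia during the study of further subjects could be done using the local normal ranges", which would lower the limit to 1.0 × 10⁹/L. If local ranges are endorsed, "the grading will be modified based on input from DSMB".

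**Protocol 8.1.1.1** makes two of these counts primary. Endpoint (d) is "Number and percentage of subjects with reported SAEs throughout the study duration". Endpoint (e) is the number and percentage with reactive arthritis or neutropenia.

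**Protocol 8.4.2.1.3** provides for a summary under one bullet, "Serious adverse events and adverse events of special interest", plus listings.

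**SAP 13.3** gives eight analysis categories for unsolicited events: any, related, leading to death, serious, related serious, leading to withdrawal, leading to dose reduction, interruption or delay, and leading to hospitalization. AESIs appear in that section only as events to be recorded.

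**The concern.** Treating every AESI as an SAE for reporting and for the second-dose decision is a defensible precaution with a novel vaccine that was followed by neutropenia in phase 1. The difficulty arises when the same label feeds a primary endpoint. Followed literally, the number of subjects with any SAE adds together two different things: events that meet a 7.1.4 criterion, and ANC values under a limit in people who may be entirely well.

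Protocol 3.7 itself says that healthy African populations have lower neutrophil counts than western ones, so some low values are to be expected without any vaccine effect. Because the limit can change after the first 18 subjects, the absolute count also depends partly on a DSMB recommendation about reference ranges. A reader of the study report who sees a percentage with SAEs cannot tell from that figure how much of it is clinical. The related-SAE count has the same problem.

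**Working it through.** **The plan's own figures.** No stated figure depends on this point. The two that exist reproduce: P(at least one event) with n = 20 and a rate of 10% is 1 − 0.9²⁰ = 0.878 (stated 87%), and 20/(1 − 0.15) = 23.5, rounded up to 24 per group (stated 24).

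**Following one event through the text.** Take a subject with ANC 1.6 × 10⁹/L at day 7, no symptoms, limit 1.8.

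1. 7.1.4: if no criterion is met, the event is non-serious.
2. 3.7 and 7.1.4.1: ANC is below the limit, so the event is an AESI.
3. 7.1.4.1: an AESI is categorized as an SAE.
4. 8.1.1.1(d): the subject counts as having a reported SAE.
5. SAP 13.3: the subject enters the SAE category, and the related-SAE category if judged possibly or probably related. Nothing marks the event as failing 7.1.4.
6. With a 1.0 limit, the same value is not an AESI and the subject is not counted.

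**What the existing categories separate.** Death and hospitalization in SAP 13.3 isolate two of the six criteria. Life-threatening, disabling, congenital and medically important events are not isolated. The shift tables in SAP 13.5 are by time point and use the site laboratory's range (SAP 8.8), which need not equal 1.8 or 1.0, so they do not give a subject-level AESI count.

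**Size, illustration 1 (all rates assumed).** One group of 24, with a 1% true rate of 7.1.4 events and independent neutropenia at rate q. The combined rate is c = 1 − 0.99(1 − q), the expected count is 24c, and P(at least one) is 1 − (1 − c)²⁴.

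| q | expected subjects with an SAE | P(at least one) |
|---|---|---|
| 0 | 0.24 | 21% |
| 5% | 1.4 | 77% |
| 10% | 2.6 | 94% |
| 20% | 5.0 | 99.6% |
| 30% | 7.4 | >99.9% |

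**Size, illustration 2 (simulation).** From 3.7: the local interval 1.0–5.3 and the limits 1.8 and 1.0. Assumed: lognormal ANC, that interval read as the central 95%, equal correlation r between draws, four scheduled post-vaccination draws, no vaccine effect, no dropout. Log-mean = (ln 1.0 + ln 5.3)/2 = 0.834; log-SD = (ln 5.3 − ln 1.0)/(2 × 1.96) = 0.425. Probabilities are conditional on passing screening at the limit in force. In the switch scenario the first 18 are judged at 1.8 on day 7 and at 1.0 afterwards, and the other 54 at 1.0 throughout. For example, at r = 0.5: 18 × 0.202 + 54 × 0.068 = 7.3.

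| r | 1.0 limit: P, of 72 | switch: P for first 18, total of 72 | 1.8 kept: P, of 72 |
|---|---|---|---|
| 0.5 | 0.068, 4.9 | 0.202, 7.3 | 0.456, 32.8 |
| 0.65 | 0.055, 4.0 | 0.164, 5.9 | 0.370, 26.6 |
| 0.8 | 0.040, 2.9 | 0.121, 4.3 | 0.269, 19.4 |
| 0.9 | 0.026, 1.9 | 0.084, 2.9 | 0.184, 13.2 |

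With 1.8 kept, between 93% (r = 0.5) and 99.9% (r = 0.9) of the affected subjects never fall below 1.0. A rerun with fresh random numbers agreed to within about 0.1 subject.

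**The case against.** The strongest reply is that the mixing can be undone from the planned outputs. SAP 13.3 tabulates by system organ class and preferred term, so neutropenia would have its own row. Protocol 8.4.2.1.3 requires listings by subject, and with 72 subjects these can be read one by one. Deaths and hospitalizations have their own categories. All of this stands, and it limits the problem to the subject-level any-SAE and related-SAE counts.

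The concurrent 1:1:1 control arm also matters. The limit in force does not differ by arm, so background low ANC should fall about equally across groups. A reader might infer that the between-group comparison is biased. The documents do not support that: a change of limit moves the absolute count in all arms and does not by itself create a difference.

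One could read the words in 3.7 about a reporting perspective as confining the rule to expedited reporting. But 7.1.4.1 covers categorization as well as reporting, and no text keeps these events out of the SAE count.

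On endpoint (e), a reader might infer that AESIs have no planned analysis. That goes too far. Protocol 7.1.4.1 and 8.4.2.1.3 promise a summary and listings, SAP 13.3 does not revoke them, and SAP 17 refers to a full table list that is not among these documents. The SAP may also lag the protocol: SAP 14.1 plans no interim analysis, whereas Protocol 8.6 now does. What remains is an SAP that does not carry forward a protocol commitment. Even a separate AESI table would not show which of the counted SAEs meet 7.1.4.

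**Conclusion.** The point holds for the top-line counts. As written, the any-SAE and related-SAE subject counts for primary endpoint (d) would combine laboratory neutropenia with events meeting 7.1.4, and the absolute figure would depend on whether 1.8 or 1.0 applies. This follows from the definitions and needs no assumption.

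The size does need assumptions. The documents give no neutropenia rate, and the phase 1 cases (two grade 3, six grade 2) come without a denominator. The simulated ranges (about 2–5, 3–7 and 13–33 of 72) rest on an assumed distribution and correlation, and do not model exclusion criteria 22 and 23. They show the mechanism and are not a forecast. The largest figures arise only if 1.8 is kept for everyone.

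A reader might also infer a threat to a statistical conclusion or to subject protection. There is none here: no hypothesis is tested, and the neutropenia hold in 3.6 uses ANC cut-offs and fever, not the SAE count. Nor does the point show the AESI-as-SAE rule to be wrong as a precaution. The harm is to interpretation of a descriptive primary endpoint. Severity is minor to moderate. The missing AESI category in SAP 13.3 is a secondary alignment gap.

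**What to change.** Change the analysis only. Leave the rule in 7.1.4.1, the reporting duties in 7.1.5 and the second-dose rules in 3.7 and 3.9 as they are.

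1. Before unblinding, record for each AESI whether it meets a 7.1.4 criterion, and which one.
2. In SAP 13.3, give the subject counts for any SAE and for related SAEs by vaccine group in two forms: as categorized under 7.1.4.1, and restricted to events meeting 7.1.4.
3. As an alignment with Protocol 7.1.4.1 and 8.4.2.1.3, add to SAP 13.3 an AESI summary for endpoint (e) by vaccine group: reactive arthritis, and neutropenia by grade, with the limit and grading scale that applied stated in the table.

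The cost is one flag per AESI if the safety forms do not already record it, a few rows in the SAE tables and one further table. Sample size is untouched. The drawback is that the report must explain two SAE counts side by side.

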3.6 Stopping/Pausing Guidelines

At the end of the 7 days observation period following 1st vaccination of the initial 18 subjects, a summary of all safety data (solicited local and systemic AE, unsolicited AE and SAE), listings of hematology, blood chemistry and urine dipstick/ urinalysis test values and respective clinically significant modifications, if any, will be provided to the DSMB. Based on evaluation of the safety data, the DSMB will make a recommendation, as to whether the enrollment can be completed or not. Additionally, DSMB will make a recommendation, as to whether the enrollment of further subjects could be done using the published local normal ranges for neutrophils in Africa (Karita et al., 2009) or should instead be continued using the western normal ranges adopted for the first 18 subjects. Enrollment for the subsequent subjects will be started immediately after DSMB review and confirmation in writing.

During the course of the study, the occurrence of two cases of marked neutropenia (i.e. $< 0.5 \times 10^9/L$), or of febrile neutropenia (i.e., ANC $< 1.0 \times 10^9/L$ associated with fever) will result in study hold, unblinding of data by DSMB (but not by the investigators in the site), discussion of results with safety management team (i.e., Pharmacovigilance) and final decision made in consultation with DSMB, IRB and PI. For additional information, please refer to [Section 3.7, Procedures Related To Neutropenia](#)

Independent of the DSMB, GVGH, as a sponsor, retains the right to halt the study at any time if there is a safety concern. If the study is prematurely terminated, the sponsor will promptly inform Regulatory Authorities and Ethic Committees on the decision of stopping the trial and no further enrollment or study immunizations will occur until written authorization is provided by the sponsor in conjunction with a recommendation to proceed by the DSMB and in consultation with Regulatory Authorities and Ethic Committees, as appropriate.

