3.9 Premature Withdrawal from Study

Subjects may withdraw at any time, or be dropped from the study at the discretion of the investigator should any untoward effects occur and/or for safety reasons. In addition, a

subject may be withdrawn by the investigator or the Sponsor if he/she violates the study plan or for administrative reasons. The investigator or study coordinator must notify the Sponsor immediately when a subject has been withdrawn due to an adverse event.

The circumstances above are referred to as premature withdrawal from the study, and the reason for premature withdrawal should be clearly documented and detailed in the source documentation. The investigator should make every attempt to evaluate the subject's safety, including resolution of ongoing AEs, at the time of premature withdrawal. If a subject wants to withdraw from the study before all doses are administered or prior to the last planned study visit, the subject will be asked to be followed for safety for the duration of the study. When a subject withdraws, or is withdrawn, from the study, the procedures described in [section 5.5.1, Early Termination Visit](#) should be completed if possible.

The reasons for premature withdrawal from the study include: Adverse event, death, withdrawal of consent, lost to follow-up, administrative reason, and protocol deviation. These reasons are described in greater detail below.

Adverse Event

For any subject withdrawn from study participation prior to the planned Study Termination Visit, it is important to determine if an AE was associated with the reason for discontinuing the study. This AE must be identified on the AE CRF page by indicating "Withdrawn from study due to AE". Any ongoing AEs at the time of study withdrawal must be followed until resolution or stabilization.

Subjects who develop a serious adverse event (SAE) judged to be possibly or probably related to the study vaccine, including hypersensitivity reactions, should not receive subsequent vaccination.

Death

For any subject withdrawn from study participation due to death, this should be noted on the Study Termination CRF page and the associated SAE that led to the death must be reported.

Withdrawal of consent

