Any subject who becomes pregnant during the study, despite the protocol requirement for adequate contraception, will not receive further vaccination but should be encouraged to continue participating in the study for safety follow-up. The site must complete a paper Pregnancy Report CRF (initial report) as soon as possible after learning of pregnancy occurrence (see [section 7.1.6, Pregnancies](#) for further details). If the subject withdraws from the study for any of the above categories except death, the site will obtain permission from the subject to continue to remain in contact with her until the outcome of the pregnancy is known, even if the outcome is not known until after the subject reaches the end of follow-up period.

Refer to [section 3.6, Stopping/Pausing Guidelines](#) and to [section 3.7 Procedures related to neutropenia](#) for further details in case of neutropenia.

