4.2 Exclusion Criteria

1. Individuals with behavioral or cognitive impairment or psychiatric disease that, in the opinion of the investigator, may interfere with the subject's ability to participate in the study.
2. Individuals with any progressive or severe neurological disorder, seizure disorder or previous Guillain-Barré syndrome.

¹ A subject is considered to be compliant if the Investigator judges that the subject will return for all the follow-up visits as scheduled in the study.

² The following birth control methods are considered effective:

- Hormonal contraceptive (such as oral, injected or implantable contraceptives) if used for at least 2 months prior to 1st vaccination

3. Individuals who, in the judgment of the investigator, may not be able to comply with all the required study procedures.
4. Individuals with history of any illness that, in the opinion of the investigator, might interfere with the results of the study or pose additional risk to the subjects due to participation in the study.
5. Individuals with history of reactive arthritis.
6. Individuals with known HIV or hepatitis B virus infection or HIV related disease, history of an autoimmune disorder or any other known or suspected impairment /alteration of the immune system. Individuals under systemic administration of corticosteroids (PO/IV/IM) for more than 14 consecutive days within 90 days prior to screening.
7. Individuals with a known bleeding diathesis, or any condition that may be associated with a prolonged bleeding time.
8. Individuals with a neutrophil count lower than $1.8 \times 10^9/L$ (applicable to the initial 18 subjects) or lower than $1.0 \times 10^9/L$ (applicable to the additional subjects if approved by DSMB) at screening
9. Individuals with any serious chronic or progressive disease according to judgment of the investigator (e.g., neoplasm, insulin dependent diabetes, Type 2 diabetes mellitus, hypertension, cardiac, renal or hepatic disease and tuberculosis).
10. Individuals who have any malignancy or lymphoproliferative disorder.
11. Individuals with history of allergy to vaccines components or any other allergies deemed by the investigator to increase the risk of an adverse event if they were to participate in the trial.
12. Individuals participating in any clinical trial with another investigational product within 28 days prior to the screening study visit or intent to participate in another clinical study at any time during the conduct of this study.

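### Section 3.7 has no individual dose-2 stop, independent of causality, for febrile neutropenia at ANC 0.5 to <1.0 x10^9/L

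*Protocol*

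**What the plan says.** - **Protocol 3.7.** If the ANC after dose 1 is below 0.5 x10^9/L, "the subject will be immediately discontinued from 2nd vaccination". The same stop stands in both subset paragraphs and does not depend on cause. From 0.5 up to the applicable lower limit (1.8 western, 1.0 local) the section asks only for weekly repeat counts. It adds that neutropenia of any grade "will be considered as Adverse Events of Special Interest (AESI) from a reporting perspective".
- **Protocol 7.1.4.1.** Neutropenia is any ANC below the lower limit of normal, and "All AESIs occurring during the study will be categorized and reported as a SAE".
- **Protocol 3.9.** The bar on further doses covers "Subjects who develop a serious adverse event (SAE) judged to be possibly or probably related to the study vaccine". It has no severity threshold. The section ends by sending the reader to 3.6 and 3.7 "for further details in case of neutropenia".
- **Protocol 3.6.** One trigger is two cases of ANC below 0.5. The febrile trigger is an ANC below 1.0 "associated with fever) will result in study hold, unblinding of data by DSMB". The action is at study level.
- **Protocol 4.3.** A temperature of 38.0 C or above in the 3 days before vaccination is a reason to delay. The section has no ANC rule. Section 6.3 points to 4.3 for dose-2 eligibility and also requires that vaccination be clinically appropriate in the investigator's judgment.
- **Protocol 4.1 and 4.2.** Entry criteria are rechecked before dose 2. They include good health on haematology and clinical judgment (inclusion 4) and unreasonable safety risk in the investigator's opinion (exclusion 21). Exclusion 8, which begins "Individuals with a neutrophil count lower than", is tied to screening.
- **Amendment 2, rationale.** The sponsor's precaution for future protocols discontinues subjects with neutropenic fever or an ANC below 500/mm3. The form then says most of the precautions are already in this protocol and names two that are not. Neutropenic fever is not one of the two.

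**The concern.** The plan treats febrile neutropenia as serious enough to hold the whole study. Yet the section that governs neutropenia in the individual does not mention fever. A subject with an ANC of, say, 0.7 and a fever a week after dose 1 could be offered dose 2 three weeks later if the event was judged not related. That is first a question of subject safety.

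It also touches the data. Neutropenia is part of the primary safety endpoint (8.1.1.1, item e), and whoever is or is not given dose 2 determines in whom neutropenia after dose 2 can be observed. A dosing rule of this kind should not vary with the investigator's causality call.

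**Working it through.** The plan gives no figure on this point, so the check sets the rules side by side.

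**1. Rule table for dose 2, by case after dose 1** (ANC in 10^9/L; LLN = applicable lower limit)

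| Case | 3.7 | 3.9 with 7.1.4.1 | 3.6 |
|---|---|---|---|
| ANC <0.5 | stops | stops if related | hold at two cases |
| 0.5 to <1.0, fever, related | silent | stops | hold at one or two cases |
| 0.5 to <1.0, fever, not related | silent | does not apply | hold at one or two cases; subject's outcome not stated |
| 0.5 to <LLN, no fever, related | silent | stops | no |
| 0.5 to <LLN, no fever, not related | silent | does not apply | no |

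The third row is the gap. Automatic individual stops there: 0 from 3.7 and 0 from 3.9. Even if such a case is serious in its own right under 7.1.4 (hospitalization, for example), 3.9 still requires relatedness.

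**2. Does the gap depend on the DSMB's choice of range?** No. An ANC below 1.0 is below both lower limits (1.8 and 1.0), so the third row reads the same for the first 18 subjects and the later 72 - 18 = 54.

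**3. Does the fever delay in 4.3 close it?** Dose 2 is due 28 days after dose 1, with a window of 0 to +7 days. A fever on day 7 after dose 1 lies 28 - 7 = 21 days before the earliest dose 2 and 35 - 7 = 28 days before the latest. The look-back is 3 days. Even inside it, the consequence is delay, not a stop.

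**4. Does 3.6 close it?** The sentence can be parsed two ways. If the number two governs both limbs, a first febrile case does not hold the study. If it governs only the ANC <0.5 limb, one febrile case does. On either parsing, nothing says whether the affected subject may have dose 2 once a hold is lifted.

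**5. Does the recheck before dose 2 close it?** Inclusion 4, exclusion 21 and 6.3 give the investigator grounds to withhold, but each rests on judgment. Exclusion 8 would bar regardless of cause only if read as the current count, against its tie to screening, and only while the Visit 3 count is still low. A recovered count passes.

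**6. What do the Phase 1 counts add?** Section 1.1 reports 2 grade 3 and 6 grade 2 cases, 2 + 6 = 8, all clinically asymptomatic. They say nothing about febrile cases. For afebrile cases, assume the grade bands printed in Amendment 2 (grade 2: 1.0 to <1.5; grade 3: 0.5 to <1.0) and that all 8 were judged related. Section 3.7 alone stops 0 of 8. Sections 3.9 with 7.1.4.1 stop 8 of 8 at a lower limit of 1.8 and 2 of 8 at 1.0. This only restates the thresholds. Arm, dose number, causality and denominator are not given, so no rate follows.

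**The case against.** The strongest reply is that the gap is narrow. Under 7.1.3 an event is possibly related if the timing is reasonable and vaccine or another cause could explain it. Many febrile neutropenias soon after dose 1 would meet that and be barred by 3.9. What is left is mainly cases with a clear alternative cause, and there an investigator may reasonably want discretion. Discretion exists in inclusion 4, exclusion 21 and 6.3; the DSMB is consulted on any safety issue (3.8); and a single febrile case may already trigger the hold. The Amendment 2 precaution on neutropenic fever is worded for future protocols, with particular attention to children, so its absence here may be deliberate.

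Most of this stands, and it limits the point to cases not judged related. It does not remove it. Discretion is not a rule, and the hold does not settle the individual's dose. Amendment 2 is cited for intent only, not as an error in the form: having quoted the precaution, the form checks this protocol against the list and does not name neutropenic fever as missing, which suggests it was thought to be covered.

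A reader might infer that febrile cases at 0.5 to <1.0 have no automatic stop at all, or that the hold needs two of them. The documents support neither: 3.9 bars related cases, and 3.6 can be read as one case.

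**Conclusion.** The point holds in this limited form. For febrile neutropenia at ANC 0.5 to <1.0 judged not related, no automatic rule stops the individual's second dose, and the decision rests on judgment. This is an omission in wording, not a calculation error. How many subjects it would affect cannot be estimated. The conclusion assumes fever outside the 3 days before dose 2 and exclusion 8 read as worded.

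A secondary point is open but has no single right answer. For related, afebrile, non-serious neutropenia from 0.5 to below the lower limit, 3.9 with 7.1.4.1 bars dose 2 while 3.7 is silent, and no sentence gives either precedence. The band runs to 1.8 where "the more conservative western normal ranges will be adopted for ANC collected up to 7 days after 1st vaccination of the initial 18 subjects" applies, and to 1.0 for later subjects if local ranges are adopted. A reader might infer that the sections contradict each other. They do not: silence is not permission, and applying 3.9 satisfies both. Nor do the texts settle that 3.7 governs. The reporting qualifier in 3.7 and the cross-references to it lean that way, without saying so.

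**What to change.** 1. In both subset paragraphs of Protocol 3.7, change the dose-2 stop to: *ANC less than 0.5 x10^9/L, or ANC less than 1.0 x10^9/L with fever (axillary temperature 38.0 C or above), after 1st vaccination*. The ANC limit is the one 3.6 already uses for febrile neutropenia, and the temperature is the fever threshold in 7.1.1.
2. In Protocol 3.6, write the number of febrile cases that triggers the hold: one, or two.

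Cost: a protocol amendment approved by the sponsor, the IRB/EC and, where required, health authorities (13.4), and an occasional additional missed second dose. There are no new visits, samples or subjects. A subject who misses dose 2 stays in the Overall Safety Set but leaves solicited safety set #2 (SAP 7.5). Under Protocol 8.3.6 the subject also leaves the modified FAS after dose 2; SAP 7.6 does not repeat that exclusion.

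Put the secondary point to the DSMB rather than settling it in this change. Letting 3.7 govern gives up the 3.9 stop for related afebrile cases; letting 3.9 govern withholds dose 2 for asymptomatic, even resolved, counts. Restricting exclusion 8 to the screening ANC has its own price: it removes a possible bar at Visit 3 that does not depend on causality.
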